4.3.2. Randomization

Randomization treatment assignment takes place during the Baseline-I visit after eligibility has been determined and the consent forms have been signed by the patient. In some cases randomization can occur on the same day that patient is screened for enrollment, if the patient signs the consent form on that day. If the patient wishes to come back at a later time to sign the consent forms, randomization will occur on the date they return. If a patient returns to sign the consent and enroll on a different date to his or her screening visit, he or she must have had the relevant laboratory tests within 4 weeks prior to enrollment for trial eligibility.

After obtaining the written consent, the study coordinator will assign the next identification number from the patient ID list. The coordinator will then log into the REDCap database to perform the randomization for the corresponding patient ID. The coordinator will take note of the treatment assigned by REDCap, dispense the assigned treatment to the patient, and review dosing instructions with the patient.

4.3.3. Procedures for data collection

Required study procedures include the following:

- Medical and Treatment History
- Clinical eye exam
- Visual acuity exam
- Optical Coherence Tomography (OCT)
- Fundus photography
- Laboratory measurements
- Health-related quality of life questionnaire
- Vision-related quality of life questionnaire(s)

4.3.4. Specimens

The following specimens will be collected for laboratory measurements *within 4 weeks prior to enrollment*:

- Blood for complete blood count (CBC with differential, limited to percentages of neutrophils and lymphocytes)
- Blood for CD4 at [REDACTED] sites only
- Blood for serum chemistry panel (AST, ALT, creatinine)
- Blood or urine pregnancy test (all female patients, excluding those that are post-menopausal)

The following specimens will be collected for laboratory measurements *within 90 days prior to enrollment*:

- Hepatitis B surface antigen (HBsAg)
- Hepatitis C antibody
- Tuberculin skin test
- Interferon gamma release assay
- Chest radiograph
- Syphilis (RPR/VDRL/other non-specific)
- Syphilis (FTA-ABS/MHATP/other specific)

4.3.5. Forms for data collection

The following forms will be filled out as part of the Baseline-I visit:

- Patient Consent Forms
- Eligibility/Screening Form
- Baseline History Form
- Clinical Eye Exam Form
- Secondary Clinical Eye Exam Form
- Right Eye Visual Acuity Form
- Left Eye Visual Acuity Form
- OCT Form
- Fundus Photography Form
- Laboratory Report Form
- Quality of Life Questionnaire Forms
- Treatment Assessment Form
- Protocol Deviation Form (if applicable)

4.4. Follow-up visits

It is strongly encouraged for all follow up data to be collected within the study visit window, but should be collected regardless.

All Phase II procedures and protocol are the same as Phase I. For Phase I patients who are continuing on the same medication, physicians can see the patients as often as they would like. However, for purposes of this study we will only be recording information at Month 9 and Month 12, or a non-study visit that leads to treatment failure.

Laboratory test results will be collected monthly.

4.4.1. Procedures for data collection

Required study procedures include the following:

- Clinical eye exam
- Secondary Clinical eye exam*
- Visual acuity exam
- Optical Coherence Tomography
- Fundus Photography*
- Laboratory measurements
- Quality of Life Questionnaire Forms*

*Phase 1: treatment failure and 6 month visit (whichever is first), 12 month visit; Phase 2: treatment failure and 6 month visit.

4.4.2. Specimens

The following specimens will be collected for laboratory measurements:

- Blood for complete blood count (CBC with differential, limited to percentages of neutrophils and lymphocytes)
- Blood for CD4 at [REDACTED] sites only at Baseline, Month 3, 6, & 12
- Blood for serum chemistry panel (AST, ALT, creatinine)
- Blood or urine pregnancy test (all female patients, excluding those that are post- menopausal)

4.4.3. Forms for data collection

The following forms will be filled out as part of the follow-up visits:

- Clinical Eye Exam Form
- Secondary Clinical Eye Exam Form*
- Right Eye Visual Acuity Form
- Left Eye Visual Acuity Form
- OCT Form
- Fundus Photography Form*
- Laboratory Report Form
- Adverse Event Checklist
- Medication Log
- Patient Medication Calendar (to be completed by the patient)
- Treatment Assessment Form
- *Adverse Event Log (update if necessary)*
- *Quality of Life Questionnaire Forms **
- *Serious Adverse Event Narrative Form (if applicable)*
- *Patient Dropout Form (if applicable)*
- *Protocol Deviation Form (if applicable)*

*Phase 1: baseline, treatment failure and 6 month visit, 12 month visit; Phase 2: treatment failure and 6 month visit; Treatment failure anytime (study or non-study visit)

For follow-up visits, all the above procedures and forms should be completed for all patients, regardless of if they are taking the medication or compliant with study visits.

4.5. Baseline Phase II

This visit may occur on the same day as treatment failure in Phase I, if the patient proceeds directly to Phase II. If both visits occur on the same day, study coordinators will mark the Phase I visit and Phase II visit at the same time on the case report forms. However, patients have up to two weeks to come back to clinic and begin Phase II after treatment failure in Phase I. In this case, complete the Baseline Phase II form packet on the date Baseline II starts.

4.5.1. Eligibility

In Phase I, if failure is due to efficacy or tolerability or for selected cases for safety (if deemed safe by the Medical Monitor), the patient will be considered as eligible for Phase II of the study. If there is a serious adverse event in Phase I, deemed to be related to the study drug by the Medical Monitor, the patient will be declared a treatment failure. The Medical Monitor will determine if it is safe for the patient to enter Phase II. If not, the patient should still be followed for 6 months.

As in Phase I, there is no mandated separate visit for eligibility screening in Phase II. If the patient is declared a treatment failure in Phase I for any reason other than an SAE deemed to be related to the study drug (by the Medical Monitor), he/she may immediately proceed to Phase II. Any reason for eligibility failure for Phase II will be captured in the adverse event log of the last Phase I visit, thus there is no need to have a separate eligibility screening form.

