2.3.3. Exclusion criteria

Any one excludes patient:

- Any infectious cause of uveitis
- Prior immunosuppressive therapy other than corticosteroids in the past 12 months
- Prior intolerance or safety issues with methotrexate or mycophenolate mofetil
- Prior failure to control ocular or other inflammation using methotrexate or mycophenolate mofetil
- Prior biologic therapy at any time
- < 16 years of age at enrollment
- Media opacity (such as cataract and/or corneal scar) and/or extensive posterior synechiae such that examination of the posterior segment is not possible in both eyes
- Chronic hypotony (IOP < 5 mm Hg for > 3 months) in both eyes
- Periocular or intravitreal corticosteroid injection in the past 4 weeks
- Fluocinolone acetonide implant in either eye in < 3 years
- Intraocular surgery in < 30 days, or planned surgery within the next 180 days
- Best spectacle-corrected visual acuity of hand motion or worse in better eye
- Planning to conceive during the study period, pregnant or breast-feeding (blood or urine pregnancy test for all females, excluding those who are post-menopausal is mandatory within 4 weeks prior to enrollment)
- History of cancer (If a patient has a history of non-melanoma skin cancer they can still be considered for inclusion in this study, provided it is not currently active).
- Systemic autoimmune disease or ocular condition (besides uveitis) anticipated to dictate treatment course
- Abnormal CBC (\leq 2,500 white blood cells and/or \leq 75,000 platelets and/or \leq 9 hemoglobin) within 4 weeks prior to enrollment*
- Abnormal alanine aminotransferase (ALT) and/or aspartate aminotransferase (AST) \geq 2 times the upper limit of normal for the lab and/or creatinine \geq 1.5 within 4 weeks prior to enrollment
- Evidence of active tuberculosis, HIV infection, syphilis, or hepatitis B or C (patients must have a tuberculin skin test, or interferon-gamma release assay, a chest radiograph, RPR/VDRL, FTA-ABS, or other treponemal tests, Hepatitis B surface antigen and Hepatitis C antibody tests within 90 days prior to enrollment)

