- Failure due to safety:** Patients who experience abnormal lab results meeting the designated threshold of a *non-serious adverse event* (e.g. AST or ALT increasing to twice the upper limit of normal) will immediately stop taking their medication. As these abnormalities are often reversible, patients whose abnormalities are classified as non-serious adverse events (see Table 3) will be *allowed 28 days to regain eligibility*. It is recommended that these patients repeat lab tests within 1-2 weeks of the initial abnormal result to see if the results return below the designated threshold (e.g. AST or ALT less than twice the upper limit of normal). If the lab results return below the designated threshold of a *non-serious adverse event* within 28 days, patients may be re-administered the study drug per protocol or at one of the designated dose reduction levels, at the investigator's discretion.

If lab results remain at or above the threshold of a *non-serious adverse event* for 28 days, this is classified as a serious adverse event and treatment failure will immediately be declared. At this point, patients will be treated according to the best medical judgment of their clinician and not switch to Phase II (if currently in Phase I). However, month 6 visit data and imaging should still be collected (Phase I and Phase II), if the serious adverse event occurs before the six month visit. For other non-serious adverse events (such as an opportunistic infection) the study drug may be stopped temporarily as per the discretion of the investigator. If an infection does not resolve within 28 days, it is considered a serious adverse event.

Table 3: Thresholds for classifying non-serious and serious lab abnormalities

	Non-Serious Adverse Event*	Serious Adverse Event
Leukocytes	>1,000 to <2,500/ μ L	\leq 1,000/ μ L
Platelets	20,000 to 75,000/ μ L	< 20,000/ μ L
Hemoglobin	\geq 6.5 to < 9 g/dL	< 6.5 g/dL
SGOT (AST) or SGPT (ALT)	2 to <5 times the upper limit of normal of the reference range	\geq 5 times the upper limit of normal of the reference range
Creatinine	\geq 1.5 to < 2 mg/dL	\geq 2 mg/dL

*NOTE: If any non-serious lab abnormality does not resolve within 28 days, then it must be classified as a serious adverse event, and treatment failure due to safety will be declared.

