4.1.3. Non-study visits

Despite the regular follow-up outlined in the visit schedules above, it is anticipated that some patients will have inflammation that is difficult to control or be intolerant to the drug, leading to additional visits. These additional visits may not fall within the study visit window. It is possible that the circumstances leading to such visits may result in changes to oral or topical corticosteroid dose, or a declaration of treatment failure and a need for rescue treatment. If treatment failure is declared at a non-study visit, all of the forms required at the time treatment failure is declared should be completed.

Guidelines for non-study visits

- Any changes to oral or topical corticosteroid dose will be noted on the appropriate form during the next scheduled study visit.
- If a treatment failure is declared at a non-study visit during follow-up while being treated during...
 - Phase I (initial randomized treatment): Record a treatment failure using Treatment Assessment Form. Perform Baseline II visit at this time or within 14 days. Phase II rescue treatment can start immediately.
 - Phase II: Record a treatment failure using the Treatment Assessment Form. Patient should continue to be followed until 6 months and 6th month data collected.
 - If treatment failure is declared at a non-study visit, an attempt should be made to collect as much information as possible, including the forms listed in Section 4.2.

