4.6.2. Specimens

No specimens are required during non-study visits.

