4.6.3. Forms for data collection

The following forms will be filled out at non-study visits *only if treatment failure is declared*. Every attempt should be made to acquire information for all other forms. However, if this is not possible, at the minimum the following must be completed:

- Clinical Eye Exam Form
- Treatment Assessment Form
- Quality of Life
- Medication Log
- Adverse Event Checklist
- *Adverse Event Log (update if necessary)*
- *Serious Adverse Event Narrative Form (if applicable)*

5. Study examinations and procedures

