5.6. Laboratory measurements

Hematology and serum chemistry will be monitored in all patients prior to enrollment and throughout participation in the study. Each of the participating sites has an accredited onsite laboratory where all blood draws and laboratory measurements will be performed. The following will be measured and recorded on the Laboratory Report Form (Section A.8) for each:

Hematology

- Hemoglobin and/or hematocrit
- Platelet count
- White blood cell count (WBC)
 - % neutrophils; % lymphocytes
 - CD4 lymphocyte count ([REDACTED] sites only, at Baseline, Month 3, 6, & 12)

Serum Chemistry

- SGOT (AST)
- SGPT (ALT)
- Creatinine
- Serum or urine pregnancy test

Laboratory measurements used for baseline visits should be collected 4 weeks prior to enrollment. Those used for follow-up visits may be collected at any time within the study visit window. Laboratory measurements must be collected at each study visit.

All abnormal values will be reported on the Adverse Event Checklist (Section A.10) and monitored for resolution on the Adverse Event Log. Abnormalities which result in a non-serious adverse event (i.e. AST or ALT increasing to twice the upper limit of normal) will result in immediate stopping of study medications. As these abnormalities are often reversible, patients will be allowed one month to regain eligibility. If the lab results have returned to normal within one month, patients may be re-administered the study drug according to protocol. Labs can be checked prior to one month, and if normal, treatment can resume. Otherwise, treatment failure will be declared and patients may be treated according to best medical judgment of physician. They should still be followed for their 6th months visit and be treated according to the best medical judgment of their physician.

Laboratory abnormalities which meet the designated threshold of a severe adverse event (SAE) will result in immediate stopping of study medications, and should be reported on the Serious Adverse Event Narrative form (Section A.12). Treatment failure will be declared, and patients will be treated according to the best medical judgment of their physician, but still follow-up for 6 months. If a lab SAE occurs, patients will not switch to Phase II.

6. Adverse events

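### Phase II entry has no stated laboratory criterion, so a patient in the 28-day lab hold may start the second drug at a value that stopped the first

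*Combined protocol and SAP*

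**What the plan says.** Section 2.5.2 of the protocol (failure due to safety) stops study drug at once when a laboratory value enters the non-serious range of Table 3, and allows 28 days for recovery. During that hold, "It is recommended that these patients repeat lab tests within 1-2 weeks of the initial abnormal result". A value that has not recovered after 28 days becomes a serious adverse event and a treatment failure: "At this point, patients will be treated according to the best medical judgment of their clinician and not switch to Phase II". For values that are serious from the outset, Section 5.6 states: "If a lab SAE occurs, patients will not switch to Phase II".

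Section 4.5.1 makes efficacy and tolerability failures eligible for Phase II and leaves safety failures to the Medical Monitor. On the timing of the switch, it says that a patient who fails "for any reason other than an SAE deemed to be related to the study drug (by the Medical Monitor), he/she may immediately proceed". There is no screening visit and no screening form. Reasons for ineligibility are to be found in the adverse event log of the last Phase I visit.

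For failure at a non-study visit in Phase I, Section 4.1.3 says: "Perform Baseline II visit at this time or within 14 days. Phase II rescue treatment can start immediately". Section 4.6.2 says: "No specimens are required during non-study visits". Section 4.6.3 asks for all forms but adds: "However, if this is not possible, at the minimum the following must be completed". The list that follows has no Laboratory Report Form. In the Section 4.2 table that form is marked as needed only if applicable at treatment failure. It is blank at Baseline II, a column that applies when the switch falls on a later day than the failure.

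**The concern.** The permission in Section 4.5.1 depends on the reason for failure, not on the patient's laboratory state. Nothing in Section 2.5.2 suspends a declaration of futility, month-6 efficacy failure or intolerance while a non-serious abnormality is on hold, and intolerance needs no prior dose reduction. A patient with, say, ALT at 3 times the upper limit on day 5 of the hold could be declared intolerant and given the second drug that day.

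The second drug is monitored with the same tests and stopped at the same thresholds. Starting it at a stop-drug value exposes the patient to avoidable risk. It also makes a later laboratory event in Phase II hard to attribute to one drug.

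**Working it through.** **1. Does a hold value also bar enrollment?** Compare Table 3 (Section 2.5.2) with the exclusion limits (Section 2.3.3):

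| Test | Non-serious band, stops drug | Phase I exclusion | Band inside exclusion? |
|---|---|---|---|
| WBC (/µL) | >1,000 to <2,500 | ≤2,500 | yes |
| Platelets (/µL) | 20,000 to 75,000 | ≤75,000 | yes |
| Hemoglobin (g/dL) | ≥6.5 to <9 | ≤9 | yes |
| AST or ALT (× ULN) | 2 to <5 | ≥2 | yes |
| Creatinine (mg/dL) | ≥1.5 to <2 | ≥1.5 | yes |

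The result is 5 of 5.

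**2. What bars Phase II?**

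- Laboratory SAE: barred (Section 5.6).
- Non-serious value unresolved at 28 days: barred (Section 2.5.2).
- Non-serious value before day 28, with failure declared for efficacy, futility or intolerance: no bar stated, and Section 4.5.1 permits immediate entry.

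**3. How old can the labs be at a non-study failure?** Section 4.1.1 schedules monthly visits by average month length, with windows of ±15 days (month 6: −15 to +30). Section 5.6 requires labs at each study visit. Assume on-time visits with labs drawn on the visit day, and count any visit inside a window as the scheduled one.

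- Average month: 365.25 / 12 = 30.44 days.
- The next window opens 30.44 − 15 = 15.4 days after an on-time visit. A true non-study failure therefore has labs at most about 15 days old.
- Entry 14 days later: 15.4 + 14 = 29.4 days, against the 4 weeks (28 days) allowed for Phase I.
- If failures fall uniformly between visits (an assumption), the share with labs older than 28 days is 0% for same-day entry and 0% for entry 7 days later (15.4 + 7 = 22.4). For entry 14 days later it is (15.44 − 14) / 30.44 = about 5%.
- Early-visit extreme: month-5 visit 15 days early (152.2 − 15 = day 137.2), failure just before the month-6 window opens (182.6 − 15 = day 167.6). Labs are then 30.4 days old, or 44.4 with entry 14 days later.

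**4. What would a laboratory criterion do to the entry limit?** Section 4.1.2 closes Phase II entry 2 weeks after failure. For failure on hold day *d*, entry closes on day *d* + 14, while recovery is allowed to day 28. The shortfall, 28 − (*d* + 14), is positive for *d* = 0 to 13 and runs from 14 days down to 1. A criterion added without changing this limit could shut out patients who recover late in the hold.

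**The case against.** Several texts suggest that a check was intended. Section 2.5.2 describes the hold as a period for becoming eligible again. Section 5.6 stops study medication at these values and sends all abnormal values to the adverse event log, which Section 4.5.1 treats as the record of Phase II ineligibility. Section 4.4 applies Phase I procedures to Phase II. SAP Section 2.3.2 gives the second drug only to patients who meet eligibility criteria. The wording of Section 4.5.1 is permissive, and a clinician may well wait. All of this stands as evidence of intent. But none of these texts names a laboratory limit for Phase II or says that the hold on the first drug applies to the second. The log cannot show a result that was not drawn.

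On missing labs the objection largely succeeds. Sections 4.1.3, 4.6.1 and 4.6.3 ask sites to try to complete all procedures and forms when failure is declared at a non-study visit, and Section 4.6 prefers a scheduled visit. A reader might infer from the visit calendar that stale labs are common: 8%, 31% or 54% older than 28 days for entry 0, 7 or 14 days after failure, with extremes of 75 or 89 days. The shares treat the whole interval between visits as non-study time. The extremes place a non-study failure at the end of the month-6 window. Section 4.6 describes non-study visits as falling outside the windows, so these figures are not typical. What remains is that no text requires a result to be available before dispensing, and Section 5.6 lets a visit's labs be drawn on any day in its window.

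A reader might also infer that the 2-week limit already locks out held patients. As written it need not, because Section 4.5.1 lets them enter at once, and Section 4.1.2 offers a coordinating-center exception. The limit matters mainly once a criterion is added.

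**Conclusion.** The point holds for a non-serious Table 3 value unresolved within the hold. The explicit permission covers these patients, no stated rule overrides it, and the same value stops the first drug and excludes from Phase I in all five bands. Absent or pending labs at a non-study failure are a lesser gap. With on-time visits, labs would usually be at most about 15 days old at failure and about 29 at an entry 14 days later. That rests on labs being drawn at the visit and on in-window visits counting as scheduled.

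A reader might go further and infer that patients with serious or persistent laboratory toxicity can cross over. Sections 2.5.2 and 5.6 rule that out. Nor do the documents support a claim that the trial's conclusions are at risk. The number of affected patients cannot be derived, and Aims 1 and 2 are not materially affected. This is a cheap improvement for patient safety.

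**What to change.** - **Section 4.5.1:** before the second drug is dispensed, require CBC, AST/ALT and creatinine results that are available, dated within 4 weeks before Baseline II, and within the Section 2.3.3 limits. Results from the failure visit may be reused.
- **Section 4.2:** add the Laboratory Report Form to the Baseline II column.
- **Section 4.6.2:** require specimens when failure is declared at a non-study visit, but only if no qualifying result exists.
- **Section 4.1.2:** as a consequence, let held patients enter on recovery up to day 28 of the hold, even if the 2-week limit has passed. Those not recovered by then fall under the existing bar in Section 2.5.2.

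The cost is a few lines of protocol text, one form cell, an occasional repeat draw and a short wait for the result before rescue. For held patients, entry could come up to 14 days beyond the present limit.
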